## **6.6. Continued Access to Study Intervention After the End of the Study**

No intervention will be provided to study participants at the end of their study participation.

## **6.7. Treatment of Overdose**

For this study, any dose of recifercept greater than 20 mg/kg within a 7-day period will be considered an overdose.

There is no specific treatment for an overdose.

In the event of an overdose, the investigator/treating physician should:

1. Contact the medical monitor within 24 hours.
2. Closely monitor the participant for any AEs/SAEs and laboratory abnormalities for at least 5 half-lives or 5 calendar days after the overdose of recifercept (whichever is longer).
3. Document the quantity of the excess dose as well as the duration of the overdose in the CRF.
4. Overdose is reportable to Pfizer Safety **only when associated with an SAE**.

Decisions regarding dose interruptions or modifications will be made by the investigator in consultation with the medical monitor based on the clinical evaluation of the participant.

## **6.8. Concomitant Therapy**

### **6.8.1. Prohibited During the Study**

Participants may not receive any medication or procedure that may affect the growth of the long bones. This includes human growth hormone (or related medicines such as IGF-1) and surgical/interventional procedures such as limb lengthening.

Participants cannot undergo surgical procedures of the bone during the course of the trial. This includes limb lengthening, guided growth (eg, 8 plates), tibial osteotomies, spinal surgery, neurosurgical procedures, or ENT bone procedures.

### **6.8.2. Prohibited Prior Treatments.**

Participants who have received prior human growth hormone or related products will not be eligible to participate.

Any participant that has previously received an investigational medicinal product for the treatment of achondroplasia is not eligible to participate.

Past receipt of any investigational medicinal product that could affect growth may not participate.

Receipt of any other investigational medicinal product (not covered above) in the last 30 days or 5 half-lives (whichever is longer) is prohibited.

Participants may not have previously undergone any limb-lengthening surgery.

### **6.8.3. Permitted During the Study;**

Participants who experience injection site reactions may be treated with topical corticosteroids as needed. The type of treatment, dose and duration must be recorded in the eCRF.

### **6.8.4. Rescue Medicine**

There is no rescue therapy to reverse the AEs observed with recifercept, standard medical supportive care must be provided to manage the AEs.

## **7. DISCONTINUATION OF STUDY INTERVENTION AND PARTICIPANT DISCONTINUATION/WITHDRAWAL**

### **7.1. Discontinuation of Study Intervention**

It may be necessary for a participant to permanently discontinue study intervention. Reasons for permanent discontinuation of study intervention include the following:

- Non-compliance with study intervention;
- Pregnancy;
- Withdrawal of consent by parent/guardian;
- Investigator decision to withdraw;
- Death.

Note that discontinuation of study intervention does not represent withdrawal from the study. If study intervention is permanently discontinued, the participant will remain in the study to complete the final follow-up visit. See the [SoA](#) for data to be collected at the time of discontinuation of study intervention and follow-up for any further evaluations that need to be completed.

In the event of discontinuation of study intervention, it must be documented on the appropriate CRF/in the medical records whether the participant is discontinuing further receipt of study intervention or also from study procedures, posttreatment study follow-up, and/or future collection of additional information.

The decision to withdraw the participant from the study ultimately lies with the investigator. For example, occurrence of any clinically relevant sign or symptom that, in the opinion of the Investigator (or designee), warrants participant withdrawal. Additionally, if a participant

experiences a serious or intolerable AE that prevents them from continuing with study participation such as severe injection site reaction or hypersensitivity, this would be expected to lead to withdrawal.

Study intervention will be discontinued if the investigator considers that it is in the participants best interest to initiate any of the prohibited treatments described in [Section 6.8](#).

If study intervention is definitively discontinued, the participant will not remain in the study for further evaluation. See the [SoA](#) for data to be collected at the time of discontinuation of study intervention.

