	Enroll ment	M1 b	M2 b	M3	M4 b	M5 b	M6	M7 b	M8 b	M9	M10 b	M11 b	M12	M13 b	M14 b	M15	M16 b	M17 b	M18	M19 b	M20 b	M21	M22 b	M23 b	M24	Early Term/Discon.	Follo w-up
Visit Identifier	1	2	3	4	5	6	7	8	9	10	11	12	13	14	15	16	17	18	19	20	21	22	23	24	25	26	27
Days Relative to Day 1 a	1	29	61	91	121	151	181	211	241	271	301	331	361	391	421	451	481	511	541	571	601	631	661	691	721		
Visit Window (Days)	±7	±7	±7	±7	±7	±7	±7	±7	±7	±7	±7	±7	±7	±7	±7	±7	±7	±7	±7	±7	±7	±7	±7	±7	±7	±7	±7
Polysomno graphy f													X												X	X	
Tanner staging																											
CCI																											
CCI																											
Acceptability and Tolerability Questionnaire				X			X			X		X				X			X			X			X	X	
EQ-5D				X			X			X		X				X			X			X			X	X	
PK sampling g (pre-dose)				X			X			X		X				X			X			X			X	X	
Immunogenicity sampling g (pre-dose)				X			X			X		X				X			X			X			X	X	X 
CCI																											
Concomitant treatment(s)	X	→	→	→	→	→	→	→	→	→	→	→	→	→	→	→	→	→	→	→	→	→	→	→	→	→	→
Serious and non-serious adverse event monitoring	X	→	→	→	→	→	→	→	→	→	→	→	→	→	→	→	→	→	→	→	→	→	→	→	→	→	→

- Day relative to start of study intervention (Day 1).
- Remote telephone visit to caregiver to confirm receipt of drug shipment (if required), dosing diary completion, AEs/concomitant medications and contraception check.
- Data collected to reflect local regulatory requirements on date of birth, race and ethnicity.
- Examination of cardiovascular, respiratory, gastrointestinal systems and skin.
- Urine pregnancy testing is required at screening and then only for those participants who are assessed as WOCBP, urine pregnancy test with sensitivity of at least 25 mIU/ml acceptable at each month. A serum pregnancy test will be analysed from the chemistry sample taken every 3 months. Contraception check is applicable to both WOCBP and sexually active male participants.
- Sleep study to be performed only in participants with a documented current diagnosis of sleep-disordered breathing prior to enrollment. Baseline PSG data can be within 6 months prior to enrollment.

- g. CCI [REDACTED]
- [REDACTED]
- i. Follow up visit conducted by phone. If required for ADA positive participants, additional immunogenicity sampling may be required.

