#### 6.5. Dose Modification

This protocol allows some alteration from the currently outlined dosing schedule, but the maximum daily dose will not exceed 1.5 mg/kg QD.

In case a dose reduction is necessary, the study intervention will be administered as follows:

High Dose (1.5 mg/kg QD)	Participants experiencing continued tolerability issues such as injection site reactions may be reduced to 2 mg/kg BIW and then if required to 1 mg/kg QW.
Medium Dose (2 mg/kg BIW)	Participants experiencing continued tolerability issues such as injection site reactions may be reduced to 1 mg/kg QW, if persistent then participant should be discontinued.
Low (1 mg/kg QW)	Participants experiencing continued tolerability issues such as ISRs should be discontinued from the study.

Participants that have been switched to any lower dose must stay on that dose for the remainder of the study.

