## 7.2. Participant Discontinuation/Withdrawal from the Study

A participant may withdraw from the study at any time at his/her own request. Reasons for discontinuation from the study include the following:

- Refused further study procedures;
- Lost to follow-up;
- Death;
- Study terminated by sponsor.

At the time of discontinuing from the study, if possible, an early discontinuation visit should be conducted. See the [SoA](#) for assessments to be collected at the time of study discontinuation and follow-up and for any further evaluations that need to be completed.

The early discontinuation visit applies only to participants who are enrolled/randomized and then are prematurely withdrawn from the study. Participants should be questioned regarding their reason for withdrawal.

The participant will be permanently discontinued from the study intervention and the study at that time.

If a participant withdraws from the study, he/she may request destruction of any remaining samples taken and not tested, and the investigator must document any such requests in the site study records and notify the sponsor accordingly.

If the participant withdraws from the study and also withdraws consent (see [Section 7.2.1](#) for disclosure of future information, no further evaluations should be performed and no additional data should be collected. The sponsor may retain and continue to use any data collected before such withdrawal of consent.

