### 7.2.1. Withdrawal of Consent

Participants who request to discontinue receipt of study intervention will remain in the study and must continue to be followed for protocol-specified follow-up procedures. The only exception to this is when a participant specifically withdraws consent for any further contact with him or her or persons previously authorized by the participant to provide this information. Participants should notify the investigator in writing of the decision to withdraw consent from future follow-up, whenever possible. The withdrawal of consent should be explained in detail in the medical records by the investigator, as to whether the withdrawal is only from further receipt of study intervention or also from study procedures and/or posttreatment study follow-up, and entered on the appropriate CRF page. In the event that vital status (whether the participant is alive or dead) is being measured, publicly available information should be used to determine vital status only as appropriately directed in accordance with local law.

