## **8.1. Efficacy Assessments**

### **8.1.1. Anthropometric Measurements**

Anthropometric measurements for height and proportionality will be performed and reported in the eCRF. Anthropometric measurements will be performed according to a trial-specific Anthropometric Measurement Manual, which will be provided to the investigational sites. This manual will contain a detailed description on the following:

- Which measurements to perform.
- The tools/instruments to be used.
- Standard procedure for performing these measurements.

The measurements to be taken on a 3-monthly basis are:

- Standing height (length for participants <2 years of age);
- Sitting height (crown-rump length for participants <2 years of age);
- Knee height;
- Head circumference;
- Arm span;
- Body weight;
- Elbow extension angle;
- Cranial dimensions (occipito-frontal, occipito-nasal distances).

Waist and chest circumference will be measured at baseline and at final visit.

Anthropometric data will only be collected by appropriately trained individuals at the trial site and in accordance with the anthropometric measurement manual. All sites will follow a consistent, structured and documented training program. This will occur prior to trial start, through regular refresher training and at targeted retraining based on analysis of measurement data consistency at the site.

Sites will be required to make all efforts to have the same anthropometrist at each visit for each participant (longitudinal consistency) and between participants (cross-sectional consistency). As well as following the specific procedures for measurement laid out in the measurement manual, sites will be provided with the same (or exactly equivalent) equipment across all sites and will follow the specific calibration procedures.

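### Protocol 7.1 conflicts on whether a child who stops recifercept stays in the study, and the plan neither clearly requires that child's Month 24 height nor settles whether it is analysed

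*Protocol*

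**What the plan says.** **Status after stopping drug.** Protocol 7.1 first states that stopping drug is not withdrawal and that, after a permanent stop, "the participant will remain in the study to complete the final follow-up visit". It also has the case report form record "whether the participant is discontinuing further receipt of study intervention or also from study procedures", which implies that a child can stop drug and keep attending. The last paragraph of the same section says: "If study intervention is definitively discontinued, the participant will not remain in the study for further evaluation". Section 7.2.1 says that participants who ask to stop drug "will remain in the study and must continue to be followed for protocol-specified follow-up procedures". Section 6.5 uses different terms again. For the low dose, "Participants experiencing continued tolerability issues such as ISRs should be discontinued from the study"; the medium-dose row says the child is discontinued but not from what.

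**Where height is measured.** The Schedule of Activities puts anthropometry at the eight 3-monthly visits from Month 3 to Month 24 and at the Early Term/Discon. visit. It has none at Follow-up, and its footnote reads: "Follow up visit conducted by phone". Protocol 8.1.1 adds: "Anthropometric data will only be collected by appropriately trained individuals at the trial site".

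**What the analysis uses.** Protocol 9.3.2 sets the efficacy estimand as mean change in height at Month 24 whatever the compliance with drug, and leaves out withdrawals and missing values without imputation. SAP 1.1.1 repeats that exclusion. SAP 5.1.1.1 labels the strategy hypothetical and excludes data after drug discontinuation. SAP Appendix 1, for the same main analysis, includes all collected data whatever intercurrent events occurred.

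**The concern.** Two sites can each follow 7.1 and handle the same event in opposite ways: one keeps the child in the study, the other closes the child out. Neither is clearly told to measure height at Month 24, the time point of the primary efficacy endpoint.

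The analysis documents do not settle whether that height is wanted. If off-drug heights are to be used, the protocol should ask for them. If they are not, Appendix 1 and the protocol's estimand wording are wrong. As written, the choice may be made by default: a height that was never taken cannot be recovered, so only the analysis that excludes off-drug data would remain possible.

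There is also a safety side. Protocol 8.3.1 collects adverse events for at least 28 days after the last dose. That fits poorly with a sentence ending participation once drug is stopped, and safety is a primary objective.

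**Working it through.** The plan states no figure for this point, so the check is a comparison of texts with a little arithmetic for scale.

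**1. Is there one rule on status after a stop?**

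| Place | Status of the child |
|---|---|
| Protocol 7.1, earlier paragraph | Remains, to complete the final follow-up visit |
| Protocol 7.1, last paragraph | Does not remain for further evaluation |
| Protocol 7.2.1 (family asks to stop) | Remains and is followed |
| Protocol 6.5, low dose | Leaves the study |
| Protocol 6.5, medium dose | Not stated |

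Section 7.1 says permanent in one place and definitive in the other, and nothing defines these as different events. There is no single rule.

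**2. Does any route clearly lead to a Month 24 height?**

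- The Follow-up visit is by phone without anthropometry, and height is taken only at the site, so this route gives none.
- The follow-up procedures in 7.2.1 are not defined or tied to the Month 24 visit. This route is ambiguous.
- The Early Term/Discon. visit gives an exit height. Under SAP Appendix 2.1 it counts as Month 24 only if taken on Days 706 to 735. The schedule gives that visit a window of ±7 days but no target day. Assuming the window runs from the stop day, the earliest stop whose exit height can count is Day 706 − 7 = 699. After a stop on Day 1 to 698, a Month 24 height depends on the child coming back.

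**3. Is the off-drug height wanted?** The protocol estimand as worded and SAP Appendix 1 would use it. SAP 5.1.1.1 would discard it. Both SAP texts describe the main analysis on the full analysis set.

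**4. How do collection and analysis fit together?**

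| | Off-drug heights collected | Not collected |
|---|---|---|
| Include collected data (Appendix 1) | Can be run as intended | No off-drug data to include |
| Exclude after discontinuation (5.1.1.1) | Can be run | Can be run |

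Collecting keeps both options open. Not collecting leaves one.

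**5. What does a missing Month 24 height do?** In the protocol's ANOVA of change at 24 months (9.3.2), a child without that height contributes nothing. In the SAP's MMRM the child's earlier heights still count, but the Month 24 mean then rests on an assumption about the missing value that the data cannot test.

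**6. Scale.** The documents give no discontinuation rate. Applying assumed rates to the planned 63 children: 63 × 0.05 = 3.15, 63 × 0.10 = 6.3, 63 × 0.20 = 12.6, 63 × 0.30 = 18.9. That is about 3, 6, 13 and 19 children for whom a Month 24 height is not clearly required.

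**The case against.** The strongest defence is that not collecting off-drug heights is a design choice. SAP 5.1.1.1 names a hypothetical strategy and excludes those data. The protocol's reference to compliance could mean missed doses, which is how 6.4 uses the word, rather than a permanent stop. Appendix 1 speaks only of data that were collected and obliges nobody to collect more. The study is an open-label extension, and SAP 4.1 states no hypotheses. All of this is fair, and it means no claim about power or error rate is at stake. It does not remove the problem, because the SAP gives the opposite rule in its own appendix for the same analysis.

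The two sentences in 7.1 can nearly be reconciled: the child stays for one closing phone call and has no other evaluation. But the earlier paragraph also refers to further evaluations still to be completed, and 7.2.1 says such children must be followed.

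Four stronger readings are tempting and are not supported:

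- *That the protocol rules out, or nowhere asks for, a Month 24 height after a stop.* Section 7.2.1 keeps children who ask to stop, Section 8 treats adherence to the schedule as required, and the schedule has Month 24 anthropometry. The text is ambiguous rather than silent.
- *That the exit height is optional for every child who stops drug.* The qualifier in 7.2, "At the time of discontinuing from the study, if possible, an early discontinuation visit should be conducted", concerns leaving the study. For stopping drug, 7.1 points to the schedule without that qualifier.
- *That the 7.1 conflict itself costs Month 24 heights.* Neither sentence requires one. The conflict concerns status and follow-up; the uncertain Month 24 height is a related gap.
- *That the loss can be stated as a widening of the confidence interval.* Protocol 9.3.2 estimates means by dose group, so the effect depends on which groups lose children, and in the MMRM earlier heights still contribute. The documents support no such figure.

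**Conclusion.** The point stands in two parts. The conflict within 7.1, and the conflict between SAP 5.1.1.1 and Appendix 1, are plain on the text. That Month 24 heights after a stop may not be collected is a reading of ambiguous text: they are possible, but not clearly required.

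Together these leave the main efficacy analysis with two opposite rules, one of which depends on data the protocol does not reliably obtain. The size is unknown. The counts of about 3 to 19 children rest entirely on assumed stop rates of 5% to 30%, and some of those children might return for Month 24 anyway. It should be fixed, but it does not invalidate the study.

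**What to change.** 1. **Retention rule.** Delete the last-paragraph sentence of Protocol 7.1 quoted above. State one rule in 7.1, 7.2.1 and 6.5: a child who stops recifercept without withdrawing consent stays in the study off drug, completes the 28-day safety follow-up, and is asked to attend at least the scheduled Month 24 anthropometry visit.
2. **Tolerability stops.** Protocol 7.1 also expects an intolerable adverse event to lead to withdrawal. Reword this so that it leads to discontinuation of study intervention, not withdrawal from the study. Use the same term in the medium- and low-dose rows of 6.5. Without this step, children who stop for tolerability could still leave the study.
3. **SAP.** Give 5.1.1.1 and Appendix 1 the same main rule, matching the protocol wording: collected heights are included whether or not drug was stopped. Report the exclusion of data after discontinuation as a supplementary analysis. State in both places how heights after a prohibited growth-affecting treatment or bone procedure (Protocol 6.8.1) are handled.

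**Cost.** A protocol amendment, which needs IRB/EC approval before it is implemented (Protocol 10.1.1), and matching SAP edits. The Month 24 visit and its procedures already exist, but stopped children would be asked to travel to a site without receiving drug. Some families will decline, so not every height will be recovered.

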### **7.1.1. Liver and Renal Injury**

Participants who develop hepatic or renal impairment during the study may be required to discontinue the study intervention. Isolated elevations should be followed up with a repeat blood sample 7 days later.

#### **7.1.1.1. Renal Impairment**

- eGFR of <60 mL/min.

(eGFR is to be calculated using the serum creatinine based on updated “bedside” Schwartz formula for pediatric patients ( $\text{CrCL (mL/min/1.73 m}^2) = 0.413 * \text{Height (cms) / Serum cr (mg/dL)}$ ).

#### **7.1.1.2. Hepatic Impairment**

- AST  $\geq 1.5$  x ULN;
- ALT  $\geq 1.5$  x ULN.

### **7.1.2. ECG Changes**

Not applicable.

### **7.1.3. Pregnancy**

Any participant who becomes pregnant during the study will be immediately discontinued and followed up according to [Section 8.3.3](#).

### **7.1.4. Lack of Efficacy**

Not applicable.

### **7.1.5. Temporary Discontinuation**

Not applicable.

### **7.1.6. Rechallenge**

Not applicable.

## 7.2. Participant Discontinuation/Withdrawal from the Study

A participant may withdraw from the study at any time at his/her own request. Reasons for discontinuation from the study include the following:

- Refused further study procedures;
- Lost to follow-up;
- Death;
- Study terminated by sponsor.

At the time of discontinuing from the study, if possible, an early discontinuation visit should be conducted. See the [SoA](#) for assessments to be collected at the time of study discontinuation and follow-up and for any further evaluations that need to be completed.

The early discontinuation visit applies only to participants who are enrolled/randomized and then are prematurely withdrawn from the study. Participants should be questioned regarding their reason for withdrawal.

The participant will be permanently discontinued from the study intervention and the study at that time.

If a participant withdraws from the study, he/she may request destruction of any remaining samples taken and not tested, and the investigator must document any such requests in the site study records and notify the sponsor accordingly.

If the participant withdraws from the study and also withdraws consent (see [Section 7.2.1](#) for disclosure of future information, no further evaluations should be performed and no additional data should be collected. The sponsor may retain and continue to use any data collected before such withdrawal of consent.

